#### 7. **OBJECTIVES**

### 7.1 **Primary objective**

To assess the impact the addition of CESM has on patient management. The hypothesis is that CESM should afford a definitive management decision earlier in the patient pathway.

### 7.2 Secondary objectives

To compare the sensitivity and specificity of CESM with MRI. Analysis will include:

- index lesion size
- detection of additional lesions
- detection of lesions in contralateral breast
- total extent of disease
- number of false positives identified

#### 8. STUDY DESIGN

### Summary of Study Design 8.1

This study will be a sequential cohort study with participants randomised to receive either the addition of CESM or standard care. All women with lesions of suspicion 3, 4 or 5 following mammography and ultrasound will be eligible.

### **Number of Centres**

This will be a single centre study performed by members of the CBU at Addenbrooke's Hospital, Cambridge.

### Number of Subjects

We plan to include 100 subjects in this study – approximately 50 to receive CESM and 50 to receive usual care.

# Trial duration

Subjects will be recruited into the study following their routine assessment results consultation. Participation in the study will end once the patient has undergone CESM procedure and is returned to standard care. Target recruitment is estimated to take approximately 12 months and the study will end once data analysis is complete.

# Subject withdrawal criteria

Subjects that suffer ill-effects from contrast media or procedure, or are unable to complete the procedure for whatever reason, will be withdrawn from the study. Data held on subjects who are withdrawn and on those who elect to withdraw from study will not be used in analysis.

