The pathway for women randomised to receive usual care will be the same as for those randomised to receive CESM, excluding the CESM procedure, i.e. they will undergo biopsy during their initial clinic visit and results will be discussed at the MDT where a decision regarding their future management will be made.

A flowchart illustrating patient pathways during the CONTEND Study can be found in Appendix I of this document.

A proforma will be used for each case to record patient pathway, results of biopsies and MDT patient management decisions.

Staff will be asked to provide feedback on patient acceptability and ease of undertaking the CESM procedure. They will also be asked to record any incidents of note, e.g. patient related problems; impact on clinic; issues with equipment. Time taken to undertake the examination will be recorded.

In order to compare the diagnostic accuracy of CESM with MRI, CESM images and MRI images will be anonymised and read by different readers - CESM images will be reported without the knowledge of the MRI results and vice versa. Mammography and ultrasound images will be available. A completed report on a proforma will be the basis for statistical analysis.

Histopathology data collected following surgery or from core biopsy if surgery is not undertaken and will be used as the gold standard for measurement of tumour size and extent of disease. If the patient is having primary drug therapy, tumour size will be determined from the mammogram.

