# 8.4 Study Procedures

# Screening and enrolment

Patients who have been identified as suitable for the study will be approached at the routine post-biopsy consultation when their diagnosis and treatment plan is being discussed. At this meeting, patients will be given both written and verbal information about the study.

If a patient wishes to enter the study, their eligibility will be checked by a Research Radiographer or Research Nurse and signed informed consent will be obtained. The patient will then be randomised and if she is in the CESM arm an appointment will be arranged for the procedure.

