# **CESM** procedure

Patients will be given an intravenous injection (via a power injector), into their arm, of an iodine based contrast media. This type of contrast media is used routinely in CT imaging procedures and the Cambridge University Hospitals NHS Trust Patient Group Directive for its administration will be adhered to. Patients will be asked to complete the Patient Contrast Questionnaire prior to the procedure (see Appendix II) and have their creatinine level checked using a Point of Care (PoC) device in the CT department. If serum creatinine is elevated >150 mmol/l the procedure will not be performed.

Two minutes after the injection, two mammographic exposures will be taken automatically, within approximately one second of each other, in each of the standard mammographic views (RCC, RMLO, LCC, LMLO).

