# 9. SAFETY REPORTING

### 9.1 Definition of Serious Adverse Events

A serious adverse event is any untoward medical occurrence that:

- Results in death,
- · Is life-threatening,

- Requires inpatient hospitalisation or prolongation of existing hospitalisation,
- Results in persistent or significant disability/incapacity, or
- Is a congenital anomaly/birth defect.
- Other important medical events\*

\*Other events that may not result in death, are not life threatening, or do not require hospitalisation, may be considered a serious adverse event when, based upon appropriate medical judgement, the event may jeopardise the participant and may require medical or surgical intervention to prevent one of the outcomes listed above.

After injection into an artery or vein, it is uncommon (1% risk = 1-10 in 1,0000) to experience pain and discomfort

Rare effects (0.1% risk=1-10 in 10,000) include diarrhoea, irregular heartbeat, kidney problems, cough, fever, general discomfort or dizziness

Very rare (0.01%=less than1in 10,000) include seizures (fits), clouding consciousness, disturbance of senses like touch, trembling, flushing, difficulty breathing including severe breathing difficulty due to fluid in the lungs, short term brain disorders (encephalopathy), short term memory loss, coma and stupor or myocardial infarction.

Any allergic or anaphylactic reactions to the contrast media used in CESM are likely to occur soon after the injection. These will be managed according to local policies by members of the breast team. Minor reactions, e.g., skin rashes, hives (urticaria), itching (pruritus), nausea, dizziness, runny nose (rhinorrhea), brief retching and /or vomiting will be monitored until symptoms have alleviated or further action is needed.

Moderate reactions, e.g. headache, persistent vomiting, wheezing (mild bronchospasm), palpitations, facial swelling, raised blood pressure (hypertension), abdominal cramps; may require an injection of antihistamine and/or adrenaline. An emergency drugs pack will be available in the room during CESM procedures for this purpose.

In the exceptional event of a serious reaction which has the potential to be life-threatening, e.g. difficulty breathing (overt bronchospasm), chest pain, irregular heartbeat (arrhythmia), collapse, seizure, cardiac arrest; a 'crash' call will be made to summon the emergency medical team.

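### Women who react to contrast or cannot complete CESM are removed from analysis after randomisation, so the CESM-arm management result covers only women who completed it without ill-effects

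*Protocol*

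**What the plan says.** Protocol section 8.1, under Subject withdrawal criteria, sets the rule in two steps. First: "Subjects that suffer ill-effects from contrast media or procedure, or are unable to complete the procedure for whatever reason, will be withdrawn". Second: "Data held on subjects who are withdrawn and on those who elect to withdraw from study will not be used in analysis". No exception is made for the primary endpoint, and withdrawal imposed by the investigators is handled in the same way as withdrawal chosen by the woman.

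The surrounding text bears on this as follows.

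- **Order of events (8.4, Screening and enrolment):** after consent, "The patient will then be randomised and if she is in the CESM arm an appointment will be arranged for the procedure". The Synopsis orders consent and randomisation differently, but it too places CESM after allocation.
- **Comparator (section 5, Synopsis):** the usual-care pathway "will be the same as for those randomised to receive CESM, excluding the CESM procedure".
- **Pre-procedure check (8.4, CESM procedure):** if point-of-care creatinine exceeds the stated limit, "the procedure will not be performed".
- **Primary objective (7.1):** "To assess the impact the addition of CESM has on patient management". Section 6 (Rationale) adds acceptability of the test as a purpose of the study.
- **Analysis set (10.2):** all eligible subjects are analysed, but these are defined as women with MRI, CESM and surgical histopathology data.
- **Expected events (9.3):** bruising and allergic reaction to contrast will not be recorded.

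**The concern.** Both involuntary triggers arise after randomisation and can occur only in the CESM arm. A usual-care woman can leave the analysis under this rule only by choosing to withdraw. The CESM-arm result is therefore conditioned on how women responded to the intervention.

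Two routes are visible in the protocol itself.

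1. Ill-effects carries no severity limit. Section 9.1 lists rash, itching, nausea and a runny nose as minor reactions. On the plain wording, any of these removes a woman even when all four views were taken, a biopsy followed and the MDT reached a decision.
2. The creatinine check can stop CESM in a woman already allocated to it, who then counts as unable to complete the procedure.

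At stake are the primary management-impact result, which is also meant to inform the larger trial, and the acceptability aim, for which women who do not tolerate or complete the test are especially informative.

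**Working it through.** **The plan's own figure.** The Synopsis asks for 50 successful CESM examinations and about 100 women, attributing the doubling to randomisation. At 1:1, 50 / 0.5 = 100, so the figure reproduces. It allows for no failed or withdrawn examinations. With an assumed exclusion rate f, the CESM arm needed for 50 successes is 50 / (1 − f), rounded up: 53 at 5%, 56 at 10% and 63 at 20%.

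**Inputs for the illustration.** The protocol gives neither an exclusion rate nor a management-change rate. I assume 50 women allocated to CESM and a 20% change rate among those analysed. Intervals are Clopper-Pearson 95%.

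**How often the rule would apply.** The chance that at least one of 50 women is excluded is 1 − (1 − f)^50. This is 64% at f = 2% and 92% at f = 5%.

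**Case A: non-completers with no CESM-driven change.** With k excluded, the rate per allocated woman is 0.20 × (1 − k/50), against 20% reported.

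| Excluded of 50 | Reported | Per allocated woman |
|---|---|---|
| 1 (2%) | 20% | 19.6% |
| 3 (6%) | 20% | 18.8% |
| 5 (10%) | 20% | 18.0% |

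For k = 5, 9/50 (8.6 to 31.4%) becomes 9/45 (9.6 to 34.6%). If failures are instead replaced until 50 examinations succeed, precision is kept but the shift is similar: with 6 failures, 10/56 = 17.9% (8.9 to 30.4%) is reported as 10/50 = 20.0%.

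**Case B: completers who had a reaction.** Five are excluded, of whom e had a CESM-driven change. Reported: 9/45 = 20.0%. With them included: (9 + e)/50.

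| e | Rate with them included | Reported minus included (points) |
|---|---|---|
| 0 | 18% | +2 |
| 1 | 20% | 0 |
| 2 | 22% | −2 |
| 3 | 24% | −4 |
| 4 | 26% | −6 |
| 5 | 28% | −8 |

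The upper extreme, 14/50 = 28.0%, has an interval of 16.2 to 42.5%. The direction of error is undetermined. In every row, 5/50 = 10% of usable examinations are discarded.

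**Whether another section restores the data.** Section 10.2 does not. Its definition of eligible subjects requires CESM, MRI and surgical histopathology, which narrows the set further. No section provides an analysis of all randomised women.

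**The case against.** The best defence is that this is a pilot aimed at 50 successful examinations. The Synopsis words the endpoint as additional disease found by CESM, which cannot occur under usual care. Section 8.2 allows hypothetical as well as actual decisions, and 10.2 specifies no between-arm test. Yield among completed examinations suits that aim. This stands in part: such a yield is a legitimate summary. It does not justify barring the other data, given a randomised design and an objective framed as the impact of adding CESM.

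For non-completers without images, the rate per allocated woman can be rebuilt from the numbers allocated and excluded. That is correct, and Case A does exactly this. The irrecoverable loss is data from completers who reacted and from part-completed examinations that informed a decision.

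Ill-effects may have been meant narrowly. Section 9.1 says minor reactions will be monitored and does not mention withdrawal, and 9.3 leaves contrast allergic reactions unrecorded. This is a fair doubt about intention, but it does not cancel the withdrawal wording in 8.1. The term is undefined, and the three sections need to be reconciled.

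The effect is probably small. Known renal impairment is already an exclusion, so the creatinine check should stop few women. The few contrast-effect frequencies in 9.1 are about 1% or lower, although they are garbled and do not cover the listed minor reactions. One exclusion in 50 shifts the rate by 0.4 points, against an interval for 9/50 about 23 points wide (31.4 − 8.6 = 22.8). Nothing in the protocol links a reaction to additional disease, so the 8-point extreme is only a bound. All of this stands.

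Staff feedback, incident notes and disposition counts also survive, so the loss for acceptability is partial.

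**Conclusion.** The concern holds and should be fixed. This is an explicit rule, not a detail left to a later analysis plan, and a plan that analysed these women would contradict the protocol. The rule removes women after randomisation, in one arm, because of their response to the intervention, and it discards usable primary-endpoint data.

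The expected size is modest. Under the assumed 20% change rate and 50 allocated women, excluding up to five non-completers without a CESM-driven change overstates the per-allocated rate by at most 2 points. For five completers who reacted, the report lies between 2 points too high and 8 points too low. These figures rest on assumed rates. The conclusion about the rule rests on the protocol text alone.

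**What to change.** Separate stopping the procedure from discarding the data. Clinical management stays as written.

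1. **Section 8.1:** keep every randomised woman's data in her allocated arm for the management-impact analysis, unless she withdraws consent for its use. Use the MDT decision recorded on the proforma. Count no CESM-driven change only where no CESM images contributed to that decision; CESM takes four views, so a woman who stops part-way may still have a genuine CESM-driven decision. Yield among completed examinations can be shown as an additional summary.
2. **Section 10.2:** state that the set requiring MRI, CESM and histopathology applies only to the CESM-versus-MRI accuracy comparison. Otherwise it would exclude many of the same women again.
3. **Reporting and section 9.3:** report CESM completion with reasons, and contrast reactions, over all women allocated to CESM. Amend 9.3 so that these reactions are recorded, and reconcile the undefined term in 8.1 with 9.1 and 9.3.

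The cost is wording in three sections and one CRF line for completion, reason and reaction. MDT decisions are already recorded on a proforma for each case, and the planned total of about 100 need not change. Yield and tolerability may look slightly less favourable.

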# 8.2 Primary and Secondary Endpoints/Outcome Measures

The primary endpoint is the detection of additional disease that changes patient management. Analysis will be undertaken to determine the impact of CESM on patient management decisions (actual or hypothetical). These will be extracted from details recorded on the proforma.

Secondary endpoints are the sensitivity and specificity of CESM and MRI on a per lesion basis - including comparison of the maximum dimension of the index tumour - as assessed by independent readers and compared with surgical histopathology. The efficacy of each technique at detecting additional lesions and the number of false positives identified by each will also be determined.

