# **Study Participants**

Women attending CBU who have lesions of suspicion 3, 4 or 5 following routine mammography and ultrasound.

50 patients with successful CESM examinations will be required to establish the technique, study procedures and to provide sufficient data to inform further study. It is estimated, due to randomisation procedure, approximately 100 patients will need to be recruited in order to obtain this number.
Recruitment to the study is planned to run for 12 months or until sufficient number of participants has been accrued. The study will end once data analysis is complete.
To assess the impact the addition of CESM has on patient management.
To compare the sensitivity and specificity of CESM with MRI.
The detection of additional disease by CESM that changes patient management. Analysis will be undertaken to determine the impact of CESM on patient management decisions (actual or hypothetical). These will be extracted from details recorded on the proforma.
Secondary endpoints are the sensitivity and specificity of CESM and MRI on a per lesion basis – including comparison of the maximum dimension of the index tumour – as assessed by independent readers and compared with surgical histopathology.
The efficacy of each technique at detecting additional lesions and the number of false positives identified by each will also be determined. False positives will be confirmed through follow up at 6 months.
Analysis of results will inform further study, e.g. sample size and power calculations, and will include an assessment of clinical technique and study procedures from staff questionnaires.

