### **Analysis**

Analysis will be undertaken to determine the impact of CESM on patient management decisions (actual or hypothetical). These will be extracted from details recorded on the proforma.

We will also compare the sensitivity and specificity of CESM and MRI on a per lesion basis - including comparison of the maximum dimension of the index tumour - as assessed by independent readers and compared with surgical histopathology.

Analysis of results will also be undertaken in order to inform further study, e.g. sample size and power calculations, and will include an assessment of clinical technique and study procedures from staff questionnaires.

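### The primary analysis admits hypothetical as well as actual management changes with no definition or separate tally, and the protocol's two endpoint wordings disagree on whether usual care can contribute events

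*Protocol*

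**What the plan says.** Section 7.1 sets the primary objective: "To assess the impact the addition of CESM has on patient management".

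The endpoint is worded in two ways. Section 8.2 names no modality: "The primary endpoint is the detection of additional disease that changes patient management". Section 5 (Study Synopsis) does: "The detection of additional disease by CESM that changes patient management".

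Sections 5 and 8.2, and the Analysis paragraph of Section 8.4, all admit decisions of both kinds. Section 8.2 sets out to determine the "impact of CESM on patient management decisions (actual or hypothetical", and Section 8.4 repeats it: "Analysis will be undertaken to determine the impact of CESM on patient management decisions (actual or hypothetical". Sections 5 and 8.2 add that the decisions will be taken from the proforma. Section 5 describes that form: "A proforma will be used for each case to record patient pathway, results of biopsies and MDT patient management decisions".

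On the control arm, Section 5 says: "The pathway for women randomised to receive usual care will be the same as for those randomised to receive CESM, excluding the CESM procedure". On timing, Section 8.4 (Screening and enrolment) has women "approached at the routine post-biopsy consultation when their diagnosis and treatment plan is being discussed", with consent, randomisation and the CESM appointment coming afterwards.

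**The concern.** The endpoint is disease that changes management, which is a matter of fact. The analysis then also admits decisions that were never taken. The protocol does not say what makes a decision hypothetical, who judges it, or whether it is counted with the actual decisions or apart from them.

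A change needs a before and an after. The after is the MDT decision. No before is described: nothing says that the plan on standard imaging is written down before the CESM result is seen. Without it, staff who already know the CESM result may judge in hindsight whether management changed, and for a hypothetical change there is no later record to check the judgement against.

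The kind is unlikely to be empty. On the Section 8.4 pathway CESM follows a consultation at which treatment is already under discussion, so some CESM findings may have only a hypothetical effect.

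At stake is what the pilot's main result means. The objective is the impact of adding CESM, and women are randomised to have it or not. A figure that includes hypothetical CESM-driven changes has nothing to be set against in the control arm. If the Section 5 wording governs, the same is true of actual changes.

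**Working it through.** **1. The plan's own figure.** Sections 8.1 and 10.1 give about 100 participants to provide 50 with CESM. Under the roughly equal allocation in Section 8.1, N = 50 / 0.5 = 100, which agrees. The protocol gives no management-change rate, effect size, alpha or power for the primary endpoint, so there is no power calculation to reproduce.

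**2. Which events can occur in which arm.** Usual care is the same pathway without CESM. MRI is done in either arm where standard practice calls for it (Section 5).

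| Event | Section 5 wording, CESM arm | Section 5 wording, usual care | Section 8.2 wording, CESM arm | Section 8.2 wording, usual care |
|---|---|---|---|---|
| Actual change | possible | impossible | possible | possible (for example through MRI) |
| Hypothetical CESM-driven change | possible | impossible | possible | impossible |

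The hypothetical kind is one-sided under both wordings. The actual kind is one-sided only under Section 5.

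**3. Direction.** Let A be the number of CESM-arm women with an actual change and H the number with a hypothetical change only. A combined count is A + H, and A + H ≥ A always. This needs no assumption beyond counting the two together.

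**4. Size within the CESM arm (assumed counts).** Exact (Clopper-Pearson) 95% intervals with 50 women:
- A = 5, H = 0: 5/50 = 10% (3.3% to 21.8%)
- A = 5, H = 5: 10/50 = 20% (10.0% to 33.7%)
- A = 5, H = 10: 15/50 = 30% (17.9% to 44.6%)

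**5. Size if the arms were compared (assumed rates).** This uses the Section 8.2 wording. Let the actual-change rate be a in both arms, so that the true difference is zero, and let h be the share of CESM women with a hypothetical change only. The apparent difference is (a + h) − a = h, and the apparent ratio is (a + h)/a. The last column is the probability that a two-sided 5% Fisher exact test rejects with 50 per arm. The protocol names no such test for this endpoint.

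| a | h | Apparent CESM rate | Ratio | Rejection |
|---|---|---|---|---|
| 5% | 0 | 5% | 1.0 | 0.7% |
| 5% | 5% | 10% | 2.0 | 6.3% |
| 5% | 10% | 15% | 3.0 | 24.4% |
| 5% | 20% | 25% | 5.0 | 74.8% |
| 10% | 0 | 10% | 1.0 | 1.8% |
| 10% | 5% | 15% | 1.5 | 6.1% |
| 10% | 10% | 20% | 2.0 | 19.5% |
| 10% | 20% | 30% | 3.0 | 64.0% |
| 20% | 0 | 20% | 1.0 | 2.8% |
| 20% | 5% | 25% | 1.25 | 5.9% |
| 20% | 10% | 30% | 1.5 | 15.5% |
| 20% | 20% | 40% | 2.0 | 51.5% |

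Under the Section 5 wording the usual-care rate is zero by definition, so the apparent difference is a + h, and it is not zero even when h = 0.

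**6. The proforma.** Section 5 lists pathway, biopsy results and MDT decisions. It mentions neither a plan made before CESM nor an entry for a hypothetical decision, although Sections 5 and 8.2 say that decisions of both kinds will be extracted from it.

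**The case against.** A reader might infer that the protocol pools the two kinds, that the measured impact is therefore inflated, and that it is invalid as a comparison with usual care. The documents do not support that much.

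- **Pooling is not stated.** The wording allows two tallies as easily as one, and the layout of the tabulation could be left to an analysis plan. This stands, and it makes the excess conditional.
- **No arm comparison is stated for this endpoint.** Section 10.2 names only CESM against MRI, in patients who have CESM, MRI and surgical histopathology, a set that as written leaves out usual care. This stands too. But it sharpens the question of what the control arm contributes to a primary objective about adding CESM.
- **The asymmetry is not peculiar to hypothetical changes.** Under Section 5 actual changes are one-sided as well. This stands, so removing the word hypothetical would not by itself cure the problem.
- **The proforma is not shown, and on the Section 8.4 pathway a plan is already under discussion before CESM.** The form may therefore hold that plan. This stands in part: nothing says that the plan is written down before the CESM result is known, and the Section 5 pathway, where CESM may take place at the initial clinic visit, is less clear about any earlier plan.

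A reader might also infer that the Phase 2 sample size would be set wrongly as a direct result. The protocol says the results will inform sample size and power calculations, but not that Phase 2 will be sized on a two-arm rate of management change. Section 5 calls Phase 2 a randomised trial, while Section 6 describes the planned multicentre trial as comparing the diagnostic accuracy of CESM and MRI. Any sample-size contrast would rest wholly on invented rates, so none is given here.

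The protocol itself fixes which decisions enter the primary analysis and words the endpoint in two incompatible ways. That is more than detail deferred to an analysis plan.

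**Conclusion.** The point holds in conditional form. The primary analysis admits actual and undefined hypothetical decisions with no stated separate tally, and no plan made before CESM is described as being recorded. If the two kinds are counted together, the CESM-arm figure is at least the actual-change figure, and the excess has no usual-care counterpart. The direction is certain under that condition. The size is unknown: it equals the share of CESM women with a hypothetical change only, which the documents do not give. Over assumed shares of 5% to 20% it is 5 to 20 percentage points, or 2.5 to 10 women in 50.

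Separately, and without any assumption, Sections 5 and 8.2 disagree on whether the endpoint is limited to disease found by CESM. On the Section 5 wording the randomised control arm plays no part in the primary endpoint. Both matters should be settled before the endpoint is extracted from the proformas.

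**What to change.** 1. Reconcile Sections 5 and 8.2 so that one endpoint definition stands, and one that can be measured in both arms.
2. Define the primary endpoint as an actual change in the management decision recorded by the MDT, counted alike in both arms.
3. Add one proforma field, completed in both arms, for the provisional plan on standard imaging. In the CESM arm it is written before the CESM result is shown. A change is then a difference between two written entries.
4. Define a hypothetical change and say who judges it. Report such changes separately and descriptively, for the CESM arm only. Carry this into Section 5, Section 8.2 and the Analysis paragraph of Section 8.4.

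The cost is a wording amendment and one extra proforma entry per woman. There will be fewer primary events, and so a less precise picture of what CESM might have altered, although the separate tally keeps that information. The planned 100 participants do not change.

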### Assessment of CESM images

Paired images will be examined to see if the tumour has been enhanced by the contrast media and to assess its extent. Images will also be assessed for additional foci and contralateral lesions.

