# 10.2 Analysis of Endpoints

Data from all eligible subjects will be included in the analyses. These will be patients for whom we have data from MRI, CESM and surgical histopathology.

Statistical significance of differences between CESM and MRI will be calculated using McNemar's test . Receiver operating characteristic (ROC) curves will be constructed for both imaging modalities.

Agreement between maximum lesion diameter based on CESM and MRI or CESM and histopathology will be expressed in Bland-Altman plots.

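### Per-lesion specificity for additional and contralateral findings moves with the other modality's false positives, and McNemar's test, if applied to pooled lesions, ignores that one woman can contribute several

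*Protocol*

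**What the plan says.** Protocol 8.2 fixes the unit of the accuracy endpoints: "Secondary endpoints are the sensitivity and specificity of CESM and MRI on a per lesion basis". The synopsis has the same text, and the Analysis paragraph of 8.4 repeats it: "We will also compare the sensitivity and specificity of CESM and MRI on a per lesion basis".

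The lesions in scope go beyond the index tumour. Under the objective of comparing sensitivity and specificity, 7.2 lists additional lesions, "detection of lesions in contralateral breast" and the number of false positives. Section 8.4 says of the CESM reading: "Images will also be assessed for additional foci and contralateral lesions".

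On method, 10.2 says: "Statistical significance of differences between CESM and MRI will be calculated using" McNemar's test. ROC curves are planned for both modalities. Neither is given a unit, and nothing is said about several lesions in one woman. The analysis set is limited: "These will be patients for whom we have data from MRI, CESM and surgical histopathology".

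No section says what counts as a true-negative lesion. The synopsis adds, for false positives only: "False positives will be confirmed through follow up at 6 months".

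**The concern.** There are two separate problems.

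**Specificity.** Specificity needs a list of truly negative units. The index lesion is on that list before CESM or MRI, because mammography and ultrasound found it. An additional or contralateral site that neither standard imaging, CESM nor MRI marks is never listed. Among newly found sites, a benign one therefore counts as a CESM true negative only because MRI marked it falsely, and the reverse. CESM's specificity then rises when MRI performs worse, with CESM itself unchanged. A lesion-level ROC curve has the same fault.

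**The test.** McNemar's test assumes independent pairs. If index and additional lesions are pooled, lesions in one woman share breast tissue, images and readers, and positively correlated differences make the test reject too often.

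The synopsis and the Rationale in section 6 say that the results will inform sample size and power for a later trial comparing CESM with MRI. The Rationale also hopes to show higher sensitivity and specificity than MRI. A specificity that depends on the comparator is a poor basis for either purpose.

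**Working it through.** **The plan's own figure.** Section 10.1: 50 CESM examinations / 0.5 allocated = 100 women. This reproduces. It is a feasibility number without stated alpha, power or effect. It caps the CESM-MRI comparison at about 50 women, and 10.2's data requirements together with the selective use of MRI make fewer likely.

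**1. Specificity**

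Inputs: the 52-patient study summarised in section 6 reports 13 false positives for MRI and 2 for CESM. Assumed: no overlap between them, comparator counts of 5 and 2 as alternatives, and B benign lesions known beforehand that both modalities call negative.

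With f comparator false positives, CESM specificity = (f + B) / (f + 2 + B).

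| B | f = 13 | f = 5 | f = 2 |
|---|---|---|---|
| 0 | 13/15 = 87% | 5/7 = 71% | 2/4 = 50% |
| 5 | 18/20 = 90% | 10/12 = 83% | 7/9 = 78% |
| 10 | 23/25 = 92% | 15/17 = 88% | 12/14 = 86% |

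CESM makes the same 2 errors in every cell. Benign lesions known beforehand reduce the movement from 37 points (87 - 50) to 6 points (92 - 86) but do not remove it.

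False positives per woman do not have this property: 2/52 = 0.04 for CESM and 13/52 = 0.25 for MRI, counting each reported case as one false positive.

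**2. McNemar's test on pooled lesions**

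Assumed: two-sided 5% level; each woman has 1 index lesion plus a Poisson number of additional lesions with mean 0.5 or 1.0 (overall mean 1.5 or 2 lesions); within-woman correlation rho of the CESM-minus-MRI difference from 0.1 to 0.8.

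Design effect for unequal clusters: DE = 1 + (E[m²]/E[m] - 1) × rho. True error = 2 × (1 - Phi(1.96/√DE)).

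- Mean 1.5: E[m²]/E[m] = 2.75/1.5 = 1.83. At rho 0.1, 0.3, 0.5 and 0.8, DE = 1.08, 1.25, 1.42 and 1.67, and the error is 6.0, 8.0, 10.0 and 12.9%.
- Mean 2: E[m²]/E[m] = 5/2 = 2.5. DE = 1.15, 1.45, 1.75 and 2.20, and the error is 6.8, 10.4, 13.8 and 18.6%.
- One lesion per woman, or rho = 0: DE = 1 and the error is 5.0%.

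Because the analysis set may be small, this was also simulated under the null (6,000 runs per cell). Discordance was 6% for index lesions and 30% for additional lesions, both assumed. In the cited study each modality missed 2 of 52 index lesions, so index discordance there was at most 4/52 = 7.7%. The index lesion was either independent of the others or correlated with them. Ranges run over rho 0.1 to 0.8:

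| Women | Additional lesions per woman | Asymptotic | Exact |
|---|---|---|---|
| 10-20 | 0.5 | 1.7-8.9% | 0.1-2.5% |
| 10-20 | 1.0 | 4.2-15.6% | 0.5-8.2% |
| 25-50 | 0.5 | 4.3-9.8% | 1.1-5.8% |
| 25-50 | 1.0 | 5.1-15.8% | 2.4-11.8% |

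The exact test exceeded 5% in 4 of 48 cells at 10-20 women and in 14 of 80 overall. At rho = 0 neither version exceeded 5.0%. A clustered McNemar test gave 0.2-4.1% at 10-20 women and 2.8-5.2% at 25-50. Uncorrected GEE with a robust Wald test gave roughly 5-10% at 10-20 women.

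**The case against.** The strongest reply is that this is detail for an SAP. The protocol never says that lesions will be pooled, 10.2 gives no unit for the test or the ROC curves, and 8.2 puts additional-lesion detection and false-positive counts in a separate sentence from sensitivity and specificity. That stands in part: the testing problem is conditional on pooling. It does not dispose of the specificity problem. The per-lesion unit is fixed in the protocol, and 7.2 places additional lesions, contralateral lesions and false positives inside the sensitivity and specificity comparison.

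Three stronger readings are tempting, and the documents do not support them.

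- A reader might infer that the CESM-MRI comparison itself fails. It does not. McNemar's test uses discordant pairs only, so sites negative on both modalities, listed or not, do not change it. The discordant false-positive counts remain usable for planning a paired trial.
- A reader might infer that benign index lesions are the only other negatives. Women enter after mammography and ultrasound, and readers have those images, so a benign extra lesion already seen there is also a negative that does not depend on CESM or MRI.
- A reader might infer that the test will certainly be inflated. With few women, an exact test mostly stays at or below 5%. Material inflation mainly needs the asymptotic version and many correlated additional lesions.

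It is also fair to say that lesion numbers, correlations, discordance for additional lesions and the alternative comparator counts are assumptions.

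**Conclusion.** The point holds in limited form. For additional and contralateral sites first marked by CESM or MRI, the absolute per-lesion specificity and any lesion-level ROC curve depend on the other modality. The illustration runs from 87% down to 50% with no benign lesions known beforehand, and from 92% to 86% with ten. This follows from how such sites come to be listed; only its size rests on assumptions.

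If lesions are pooled, ordinary McNemar's test can exceed its nominal level: about 6-19% in large samples, and about 2-16% for the asymptotic test with 10-20 women, under the assumed lesion numbers and correlations. There is no inflation with one lesion per woman or zero correlation.

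These are secondary endpoints of a pilot. The primary endpoint and the per-lesion sensitivity estimates are unaffected. The change should be made because the results feed the design of the next trial and the correction needs only wording.

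**What to change.** **Section 8.2.** Keep sensitivity per lesion. Restrict per-lesion specificity and ROC curves to lesions identified before CESM and MRI (index lesions and any others seen on mammography or ultrasound), and state how many are benign. For additional and contralateral findings, report the false-positive counts already planned as false positives per woman for each modality, together with the paired discordant counts.

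**Section 10.2.** For any pooled per-lesion comparison, use a score-type cluster-adjusted McNemar test (Obuchowski or Durkalski) with the woman as cluster, or GEE only with a small-sample correction. Keep exact McNemar for index-lesion comparisons with one lesion per woman.

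**Cost.** Wording only: the images, proforma and counts stay the same. No new follow-up is needed, because no negative status is claimed for unmarked tissue. The downsides are a clustered test that is conservative with few women, slightly wider intervals, and no lesion-level specificity for additional findings. The specificity that remains may rest on few benign lesions, because 10.2 requires surgical histopathology. The synopsis would accept core biopsy ("Histopathology data collected following surgery or from core biopsy if surgery is not undertaken"). As a side matter, these two sections should be reconciled.
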